5.1.2. Overall survival

Primary Estimand

Population: All patients eligible and enrolled into trial with MRT/ATRT (strata 1), osteosarcoma (strata 2), or neuroblastoma (strata 3).

Treatment: Panobinostat, dosing as per protocol.

Outcome: Estimated Overall Survival (OS). OS is calculated as the time from study enrolment to death from any cause.

Summary measure: The OS probability (Kaplan-Meier) and 95%CI will be estimated for each stratum* up to 2 years post-enrolment. Kaplan-Meier curves will be plotted for OS probability; enrolment date as start of risk period. The number of deaths and the median OS time will be reported up to 2 years post-enrolment.

**only calculated if stratum had adequate sample size (osteosarcoma and ATRT/MRT only).*

Subgroup Analysis:

As per section 5.1.1

Intercurrent Events

Potential intercurrent events:

Patient comes off study due to toxicity, or to start a new treatment.

Strategy for handling intercurrent event:

Patients coming off study due to a related toxicity or to start a new treatment will be handled with the treatment policy. OS will be analysed for all patients regardless of treatment received until last study visit.

Sensitivity Analysis

Composite Strategy

Patients coming off study due to toxicity or to start a new treatment before death could be observed will be handled by the composite strategy. The removal from study date will be treated as an event/death in sensitivity analysis.

Estimand Calculation

OS will be estimated and visualised using the Stata sts list and graph commands.

stset tvar, fail(death) origin(time enrol_date) enter(time consent_date) sts list,

strata(disease type)

sts graph, strata(disease type) tmax(24)

Median OS will be estimated using Stata stsum command *stsum,*

by(disease type)

Where time is in months and patients will be censored at their last known contact alive.

5.1.3 -Safety

Adverse events will be summarised by grade and type defined by CTCAE Version 4 from 1 week to 12 months after intervention commencement.

Relationship to study drug (definite, probable, possible) adverse events summarised in a table, with the worst AE grade reported by each participant.

A summary table of Dose Limiting Toxicities will include AE type, grade, and frequency.

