2.1 OBJECTIVES

2.1.1 PRIMARY OBJECTIVES

The primary aims of this study are as follows:

- a) To define the anti-tumour activity of low dose continuous panobinostat.
- b) To define and describe the toxicities of panobinostat for patients on a continuous dosing schedule.

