2.2 ENDPOINTS

2.2.1 PRIMARY ENDPOINTS

- a) Estimated 2-year Event free survival (EFS). EFS is calculated as the time from study enrolment to first documented disease progression, relapse or second malignancy, or death from any cause
- b) Estimated 2-year Overall Survival (OS). OS is calculated as the time from study enrolment to death from any cause.
- c) Safety, as assessed by incidence of adverse events graded according to the NCI-CTCAE, version 4.0 [Time Frame: 1 week to 12 months after intervention commencement]

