2.2.2 SECONDARY ENDPOINTS

a) Efficacy as measured by Clinical Benefit Rate (percentage of patients with stable disease or better using MRI/CT imaging) at 6 and 12 months after intervention commencement. Stable disease is defined as MRT/ATRT/Osteosarcoma with complete response (CR), partial response (PR), minor response (MR), stable disease (SD) overall response. Neuroblastoma with CR/PR/SD or Non-CR/Non-PD overall response.

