2.7 STUDY PROCEDURES

All entry requirements had to be completed during the four-week screening period before study enrolment.

Studies to be Obtained	Pre-salvage therapy ^a	Screening prior to enrolment (Baseline)	Weeks 1-4 (first 28 day course)	Subsequent Months (28 day courses)	Follow-up ^b
History (including AEs/DTs)		X	Weekly	X	X
Physical Exam (height, weight, BSA)		X	Weekly	X	X
Performance Status Refer to Appendix I		X	Weekly	X	X
Full Blood Evaluation (FBE) with Differential & Blood Film		X	Weekly	X	X
Urinalysis ^c		X	Weekly	X	
Urea & Electrolytes Calcium, Magnesium & Potassium		X	Weekly	X	X
Renal Function/GFR/Creatinine		X	Weekly	X	X
Liver Function Tests including Total Protein & Serum Albumin		X	Weekly	X	X

Thyroid Function Tests (TFTs including TSH, T3, T4)		X		End of therapy	
CT/MRI of Primary Tumour^d	X	X		2 monthly	X ^e
MRI Spine (ATRT only) Refer to Section Error! Reference source not found.	X	X		2 monthly ^f	X _{e,f}
FDG-PET/DOTATATE^g	X	X		2 monthly	X ^e
MIBG (Neuroblastoma only)		X	X	2 monthly	X ^e
CXR (ATRT only)	X	X ^h		End of therapy	
Abdominal Ultrasound (ATRT only)	X	X ^h		End of therapy	
MRI Brain (MRT only, not primary site)	X	X ^h		End of therapy	
CT Chest / CXR (Osteosarcoma only, non-lung primary)	X	X (CT and CXR)		2 monthly (CXR, CT and CXR at end of therapy)	X (CT or CXR)
Blood Samples – HDACi [Not applicable to United States]		Pretreatment	7 days after first dose		
Bone Marrow Evaluation (only if clinically indicated) including HDACi studies [Not applicable to United States]		X	End of Course	If positive at baseline or as clinically indicated	
Pregnancy Testⁱ		X			
ECG		X	End of Course	X	
Echocardiogram		X		6 monthly	

a If applicable and where available, these will be the last set of imaging investigations performed as part of routine patient care prior to salvage therapy.

b Up to 2 years from completion of therapy. c Not mandated at every time point, urinalysis performed per institutional practice.

d Use the same imaging modality throughout the course of the study e Follow-up imaging studies are not required if there is documented evidence of overt clinical progression. Follow-up imaging is 3 monthly or per routine follow-up.

f Repeat Spine MRI only if initially positive

g Use FDG-PET in non-CNS MRT.

Use FDG-PET in all osteosarcoma and neuroblastoma (if not MIBG avid).

Could be DOTATATE scans in neuroblastoma patients, when available, following discussion with Study Chair.

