3.4. DEFINITION OF BASELINE

Baseline will be defined period between consent date and date of enrolment.

Date of enrolment (day 0) will be the eligibility visit date in the database, *visdat*.

Baseline values used to define changes in measurements over time for each participant are defined as the closest to and including day 0 within the preceding 28 days. Where more than one measurement is available within this window the closest to enrolment will be used.

Patients were enrolled on the study once all eligibility requirements for the study were met. The National Coordinating Centre, in conjunction with the Study Chair, reviewed the submitted eligibility information and supporting source documentation.

Start of treatment is defined as (Week 1 Day 1 *visdat*) from the study status database.

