3.7. YEAR, MONTH AND DURATION

The following conversion factors will be used to convert days to months or years: 1 month = 30.4375 days, 1 year = 365.25 days. Duration will be calculated as (end date – start date + 1).

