6.1 MAIN ANALYSIS

6.1.1 Clinical Benefit rate

Estimand

Population: All patients eligible and enrolled into trial with MRT/ATRT (strata 1), osteosarcoma (strata 2), or neuroblastoma (strata 3).

Treatment: Panobinostat, dosing as per protocol.

Outcome: Efficacy as measured by Clinical Benefit Rate (CBR)

Summary measure: Clinical benefit rate (CBR) is the proportion of patients with an overall response of stable disease or better at MRI/CT imaging at 6- and 12-months post treatment commencement. CBR proportion (95% CI) and number will be reported for each disease strata.

Stable disease is defined as MRT/ATRT/Osteosarcoma with CR/PR/MR/SD/ overall response.

Neuroblastoma with CR/PR/SD or Non-CR/Non-PD overall response.

6- and 12- months post treatment commencement will be the overall response disease assessment closest to 6 or 12 months ($30.437 \text{ days} \times (6 \text{ or } 12) = XX \text{ days}$) after the patient first dose (day 1 course 1) or enrolled date if patient didn't start treatment.

Intercurrent Events

Potential intercurrent events:

Patient comes off study or treatment due to toxicity before an event is observed. Patient comes off study or treatment to receive another treatment.

Strategy for handling intercurrent event:

Treatment policy

CBR will be estimated for patients regardless early treatment or trial termination..

Sensitivity Analysis

Composite Strategy

Composite strategy includes early treatment termination as no benefit (not stable disease).

Calculation of Estimand

The CBR and 95%CI will be estimated using Stata's *ci proportions* command.

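### The primary adverse event window is written to open one week after treatment starts, so read literally it omits toxicities that begin and resolve in about the first week of dosing

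*SAP*

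**What the plan says.** Safety is the third of three primary endpoints and serves the second primary objective in SAP 2.1.1: "To define and describe the toxicities of panobinostat for patients on a continuous dosing schedule". The endpoint definition in 2.2.1(c) carries the tag "Time Frame: 1 week to 12 months after intervention commencement", and the analysis section, 5.1.3, repeats the window: "Adverse events will be summarised by grade and type defined by CTCAE Version 4 from 1 week to 12 months after intervention commencement".

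Section 3.4 fixes time zero: "Start of treatment is defined as (Week 1 Day 1", taken from the visit date in the study status database. In the 2.7 schedule, the row "History (including AEs/DTs" is marked weekly for weeks 1 to 4 of the first course.

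Section 5.1.3 then promises a table of treatment-related events and a table of dose-limiting toxicities. Neither sentence states a period. The SAP does not say that first-week events are included or shown separately, and it does not say which date places an event inside the window.

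**The concern.** A summary meant to describe the toxicity of a daily oral drug would normally count from the first dose. Here the endpoint and its analysis sentence agree on a later start, so an analyst finds no contrary text to fall back on. An analyst who follows the sentence literally would leave early, short-lived toxicities out of the all-event summary. The treatment-related summary states no start and could still count them. Another analyst, taking one week as the first weekly visit, would leave nothing out. The two could report different primary safety results from the same data.

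**Working it through.** The SAP gives no figure to reproduce. The check is date arithmetic, followed by the effect of one patient on a table row.

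**Inputs.** Start of treatment is Week 1 Day 1 (3.4). A course is 28 days, with up to 12 courses (2.4). Enrolment was 14 MRT/ATRT, 9 osteosarcoma and 2 neuroblastoma (section 2, Study Expansion).

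**Which days lie before the window, read literally.**
- Elapsed days: day 1 + 7 = day 8, so days 1 to 7 lie outside. That is 7/28 = 25% of the first course and 7/(12 × 28) = 7/336 = 2.1% of full treatment.
- Inclusive count, borrowing the rule in 3.7 ("Duration will be calculated as (end date – start date + 1"): 7 days is reached on day 7, so days 1 to 6 lie outside. That is 6/28 = 21% of the first course and 6/336 = 1.8% of full treatment. Nothing ties 3.7 to this boundary, so this only shows how little the counting convention matters.

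The SAP's usage elsewhere fits the elapsed count: the acetylation blood sample is timed a week after dosing begins in 2.7 and is described as a day-eight comparison in section 2.

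**What is lost depends on how events are placed.**
- By assessment date, if the first on-treatment assessment comes at about one week and looks back to first dose: no event is lost.
- By any overlap with the window: events that begin and resolve in the first week are lost.
- By onset date: every event starting in the first week is lost, even if it continues.

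**Effect on a table row.** Each patient whose only occurrence of a given toxicity falls wholly in the first week lowers that row by:
- MRT/ATRT: 1/14 = 7.1 percentage points
- osteosarcoma: 1/9 = 11.1 points
- all strata pooled: 1/(14 + 9 + 2) = 1/25 = 4.0 points

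These figures assume that every enrolled patient was dosed. The SAP does not show whether any such patient exists.

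**After the fix.** With the window opening at Week 1 Day 1, no dosing days precede it.

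**The case against.** The strongest reply is that one week names the first weekly assessment. The phrase in 2.2.1(c) is a time-frame tag, which suits a span of assessments, and the schedule does take adverse event history weekly from week 1. The clinical benefit rate supports this. Section 2.2.2 sets it "at 6 and 12 months after intervention commencement", and 6.1.1 counts to those times "after the patient first dose (day 1 course 1" but then takes the assessment nearest the target. It makes no hard cut. That reading is plausible and loses nothing. It does not settle the matter, because 5.1.3 is an instruction on what to summarise and nothing in the SAP states the look-back.

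A reader might also infer that the benefit-rate rule proves a cut at day 8. It does not, for the reason just given. That reading rests on the plain words of 2.2.1(c) and 5.1.3 alone.

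A reader might further infer that early dose-limiting toxicities are lost. The document does not support that either. The sentence on them in 5.1.3 and the Table 11 shell carry no window, and a protocol commonly sets such an evaluation period, so its absence here is no fault.

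Two further limits stand. The Table 10 shell shows no window and is titled for treatment-related events, although 9.2 lists it as a general summary, so it is uncertain which planned output would carry the late start. The mismatch in title is a separate labelling matter. The Table 10 shell also has grade columns and no stratum columns. The stratum percentages above rest on the general statement in section 4 that analysis is by stratum, and 4.0 points is the figure if rows are pooled.

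**Conclusion.** The point holds as a defect of wording in a primary endpoint. As written in both places, the window leaves out events that begin and resolve in about the first week of dosing, and no other text brings them back. Collection is unaffected; only reporting is at stake.

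The document does not show that any toxicity has been or will be dropped. The effect may be zero, either because no patient had such an event or because the analyst takes the first-weekly-assessment reading. If the literal reading is followed, the cost is 7.1 or 11.1 points per affected patient and row by stratum, or 4.0 points pooled, given that all enrolled patients were dosed. The bias could only run towards understating early toxicity.

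**What to change.** In 2.2.1(c) and 5.1.3, start the adverse event window at first dose, defined as Week 1 Day 1 as in 3.4. State that events are placed by onset date. Onset placement is one acceptable convention, but it must come with the earlier start: combined with the present one-week start it would lose the most events. With the window open from first dose, onset and overlap differ only for events that began before dosing.

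Use the same window for the all-event and treatment-related summaries. Leave the dose-limiting toxicity period as the protocol defines it.

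The cost is SAP wording in two places. No new data are needed, because the schedule already collects adverse event history weekly from week 1. Reported adverse event rates may rise slightly.

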6. SECONDARY ENDPOINTS

Measurement of effect

Evaluation of disease will be conducted by the investigator as outlined in the protocol. Stable disease will be confirmed on study entry, and tumour response determined at each imaging assessment time point. Overall response as determined by the investigator will be used for the secondary efficacy outcome analysis.

Response Assessment for Non-CNS Solid Tumours - Osteosarcoma and MRT

The revised Response Evaluation Criteria in Solid Tumours (RECIST), Version 1.1, will be used to evaluate tumour response, as assessed by medical imaging.

Overall Response for Non-CNS Tumours (Measurable Disease)

. Target lesions	Non-target lesions	New lesions	Overall response
CR	CR	No	CR
CR	Non-CR/non-PD	No	PR
CR	Not evaluated	No	PR
PR	Non-CR/non-PD/ Not evaluated	No	PR
SD	Non-CR/non-PD/ Not evaluated	No	SD
PD	Any	Yes or No	PD
Any	PD	Yes or No	PD
Any	Any	Yes	PD
Not evaluated	Non-PD	No	Inevaluable

Overall Response for Non-CNS Tumours (Non-Measurable Disease)

Non-target New Overall lesions lesions response

CR	No	CR
Non- CR/non-PD	No	Non- CR/nonPD
Not all evaluated	No	Inevaluable
Unequivocal PD	Yes or No	PD
Any	Yes	PD

Response Assessment for CNS Solid Tumours- ATRT

The Response Assessment in Neuro-Oncology Working Group's (RANO) updated response assessment criteria, will be used to evaluate tumour response. Overall response will be defined by the response of the individual components – contrast enhancing lesions, non-enhancing lesions, new lesions, corticosteroids, and clinical status per the investigator at each imaging timepoint.

Complete Response (CR)	Requires all the following criteria to be met:	
	Contrast enhancing disease	Complete Response: Complete disappearance of all measurable and non-measurable disease
	New lesions	No new lesions
	Non-enhancing lesions	Stable or improved T2/FLAIR lesions
	Corticosteroids	Patient off corticosteroids (or on physiologic replacement doses only)
	Clinical Status	Stable or improved clinically
Partial Response (PR)	Requires all the following criteria to be met:	
	Contrast enhancing disease	Partial Response: $\geq 50\%$ decrease, compared with baseline, in the sum of products of perpendicular diameters of all measurable enhancing lesions
		No progression of non-measurable disease
	New lesions	No new lesions
	Non-enhancing lesions	Stable or improved T2/FLAIR lesions on the same or lower dose of corticosteroids compared with baseline scan
	Corticosteroids	Corticosteroid dose at the time of evaluation no greater than the dose at time of baseline scan
	Clinical Status	Stable or improved clinically
	Requires all the following criteria to be met:	
Stable Disease (SD)	Contrast enhancing disease	Stable Disease: Does not qualify for complete response, partial response, or progression
	New lesions	No new lesions
	Non-enhancing lesions	Stable T2/FLAIR lesions on the same or lower dose of corticosteroids compared with baseline scan
	Corticosteroids	Corticosteroid dose at the time of evaluation no greater than the dose at time of baseline scan
	Clinical Status	Stable or improved clinically
	Defined by any of the following:	
Progressive Disease (PD)	Contrast enhancing disease	Progressive Disease: $\geq 25\%$ increase in sum of the products of perpendicular diameters of enhancing lesions compared with the smallest tumour measurement obtained at baseline (if no decrease) or best response, on stable or increases doses of corticosteroids
		Clear progression of non-measurable disease
	New lesions	Any new lesion
	Non-enhancing lesions	Significant increase in T2/FLAIR lesions on stable or increasing doses of corticosteroids, not caused by comorbid events
	Corticosteroids	N/A *
	Clinical Status	Clear clinical deterioration not attributable to other causes apart from the tumour or changes in corticosteroid dose. Failure to return for evaluation as a result of death or deteriorating condition.

* Increase in corticosteroid alone will not be taken into account in determining PD, in the absence of persistent clinical deterioration

NOTE: Patients with non-measurable disease only cannot have a complete response, the best response possible is stable disease.

Response Assessment for Neuroblastoma

The revised International Neuroblastoma Response Criteria (INRC) will be used to evaluate tumour response. Overall response will be defined by the response of the individual components – soft tissue, bone, and bone marrow disease per the investigator at each imaging timepoint..

Overall Response	Criterion
Complete Response (CR)	All components meet criteria for CR
Partial Response (PR)	PR in at least one component and all other components are either CR, MD (minimal disease, bone marrow), PR (soft tissue or bone), or not involved* (NI); no component with PD
Minor Response (MR)	PR or CR in at least one component but at least one other component with SD; no component with PD
Stable Disease (SD)	SD in one component with no better than SD or not involved* (NI) in any other component; no component with PD
Progressive Disease (PD)	Any component with PD

* Site not involved at study entry and remains uninvolved.

See Appendix VI in protocol for more detail of Tumour Response Assessment Criteria and definitions.

6.1 MAIN ANALYSIS

6.1.1 Clinical Benefit rate

Estimand

Population: All patients eligible and enrolled into trial with MRT/ATRT (strata 1), osteosarcoma (strata 2), or neuroblastoma (strata 3).

Treatment: Panobinostat, dosing as per protocol.

Outcome: Efficacy as measured by Clinical Benefit Rate (CBR)

Summary measure: Clinical benefit rate (CBR) is the proportion of patients with an overall response of stable disease or better at MRI/CT imaging at 6- and 12-months post treatment commencement. CBR proportion (95% CI) and number will be reported for each disease strata.

Stable disease is defined as MRT/ATRT/Osteosarcoma with CR/PR/MR/SD/ overall response.

Neuroblastoma with CR/PR/SD or Non-CR/Non-PD overall response.

6- and 12- months post treatment commencement will be the overall response disease assessment closest to 6 or 12 months ($30.437 \text{ days} \times (6 \text{ or } 12) = XX \text{ days}$) after the patient first dose (day 1 course 1) or enrolled date if patient didn't start treatment.

Intercurrent Events

Potential intercurrent events:

Patient comes off study or treatment due to toxicity before an event is observed. Patient comes off study or treatment to receive another treatment.

Strategy for handling intercurrent event:

Treatment policy

CBR will be estimated for patients regardless early treatment or trial termination..

Sensitivity Analysis

Composite Strategy

Composite strategy includes early treatment termination as no benefit (not stable disease).

Calculation of Estimand

The CBR and 95%CI will be estimated using Stata's *ci proportions* command.

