3.5. ASSESSMENT OF RESPONSE

The revised Response Evaluation Criteria in Solid Tumours (RECIST), Version 1.1, will be used to evaluate tumour response for non-CNS solid tumours. The Response Assessment in NeuroOncology Working Group's updated response assessment criteria (RANO) will be used to evaluate tumour response for CNS solid tumours. The revised International Neuroblastoma Response Criteria will be used to evaluate tumour response for neuroblastoma. For further details of these definitions please refer to the protocol.

The study investigator's evaluation of overall response will be used in analysis.

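### The clinical benefit lists assign MR and Non-CR/Non-PD to the wrong tumour groups, so some non-progressing patients would be scored as no benefit

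*SAP*

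**What the plan says.** SAP section 6.1.1 first defines CBR in general terms as "the proportion of patients with an overall response of stable disease or better at MRI/CT imaging", assessed at 6 and 12 months. It then spells out by tumour group which overall responses qualify. For the first group: "Stable disease is defined as MRT/ATRT/Osteosarcoma with CR/PR/MR/SD/ overall response". For the other: "Neuroblastoma with CR/PR/SD or Non-CR/Non-PD overall response". Section 2.2.2 gives the same two lists and writes MR out in full: "Stable disease is defined as MRT/ATRT/Osteosarcoma with complete response (CR), partial response (PR), minor response (MR), stable disease (SD) overall response".

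Section 6 sets out which overall responses each set of criteria can produce. RECIST 1.1 applies to osteosarcoma and MRT outside the CNS, with separate tables for measurable and non-measurable disease. RANO applies to ATRT. The revised INRC apply to neuroblastoma, and only there is MR defined: "PR or CR in at least one component but at least one other component with SD; no component with PD". Section 3.5 adds: "The study investigator's evaluation of overall response will be used in analysis".

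**The concern.** The recorded overall response goes straight into these lists, so a category that the criteria can produce but the list omits becomes a non-benefit. Each list names a category that its own criteria cannot produce, and each omits a non-progressing category that they can. This looks like a transposition. It is unlikely to be a text-extraction fault, because the same lists stand in two sections and one of them spells out MR.

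At stake is the scoring rule for the only secondary efficacy endpoint, including its composite sensitivity analysis. With strata of 14, 9 and 2 patients, one misclassified patient visibly moves the reported rate.

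**Working it through.** **Step 1. Lists against tables.** The responses in the third column are those the section 6 tables allow; the fourth column is the benefit list in 2.2.2 and 6.1.1.

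| Criteria | Applies to | Possible overall responses | Listed as benefit | Non-progressing but not listed | Listed but not possible |
|---|---|---|---|---|---|
| RECIST 1.1, measurable | Osteosarcoma, non-CNS MRT | CR, PR, SD, PD, inevaluable | CR, PR, MR, SD | none | MR |
| RECIST 1.1, non-measurable | Osteosarcoma, non-CNS MRT | CR, Non-CR/non-PD, PD, inevaluable | CR, PR, MR, SD | **Non-CR/non-PD** | PR, MR, SD |
| RANO | ATRT | CR, PR, SD, PD | CR, PR, MR, SD | none | MR |
| INRC | Neuroblastoma | CR, PR, MR, SD, PD | CR, PR, SD, Non-CR/Non-PD | **MR** | Non-CR/Non-PD |

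In the RECIST table for measurable disease, Non-CR/non-PD appears only as a non-target lesion status, not as an overall response.

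**Step 2. Who is affected.**

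- *Osteosarcoma and non-CNS MRT, non-measurable disease only.* SD and PR do not exist in that table. An evaluable patient who is neither in CR nor progressing can only be Non-CR/non-PD, which is off the list. Such a patient in CR is still counted.
- *Neuroblastoma with MR.* INRC place MR between PR and SD, so the lead sentence admits it and the list does not.
- *ATRT.* Not affected. The RANO note reads "Patients with non-measurable disease only cannot have a complete response, the best response possible is stable disease", and SD is listed.

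**Step 3. Direction.** The impossible categories add nobody and the omitted ones remove patients, so as tabulated the error can only lower CBR.

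**Step 4. Size.** Section 2 gives enrolment of 9 (osteosarcoma), 2 (neuroblastoma) and 14 (ATRT/MRT). The fall in CBR per affected patient is 1/n:

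- osteosarcoma: 1/9 = 11.1 points
- MRT/ATRT: 1/14 = 7.1 points (non-CNS MRT patients only)
- neuroblastoma: 1/2 = 50 points

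**Step 5. Illustration.** Two assumptions, neither from the SAP: 3 patients truly have benefit, and 1 of them is affected. The exact (Clopper–Pearson) 95% interval for k of n has as its lower limit the 0.025 quantile of Beta(k, n−k+1) and as its upper limit the 0.975 quantile of Beta(k+1, n−k).

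| Stratum | Benefit counted correctly | As the lists would report it |
|---|---|---|
| Osteosarcoma | 3/9 = 33.3% (7.5 to 70.1) | 2/9 = 22.2% (2.8 to 60.0) |
| MRT/ATRT | 3/14 = 21.4% (4.7 to 50.8) | 2/14 = 14.3% (1.8 to 42.8) |

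**The case against.** *The lead sentence rescues these patients.* It admits stable disease or better, and the SAP shows by its neuroblastoma list that it regards Non-CR/Non-PD as meeting that standard. For neuroblastoma MR this has force, and the point there is a conflict rather than a settled mis-scoring. For the RECIST patients it is weaker. The sentence after the lead defines what stable disease means for that group and leaves Non-CR/Non-PD out, while the RECIST tables keep it distinct from SD.

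*The answer may lie elsewhere.* Section 6 refers to protocol Appendix VI for detail. Recruitment ended in December 2021 and the SAP is dated December 2024, so the lists may have been written to match codes already recorded. This cannot be excluded from the SAP alone. It does not remove the contradiction between the SAP's lists and its tables, but it is a good reason to look at the recorded codes before rewriting the lists. If codes outside the tables were used, corrected lists applied blindly could themselves drop non-progressing patients.

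*The effect may be nil, and the endpoint is minor.* The number affected is unknown. CBR is descriptive with no test or threshold, and the intervals overlap heavily. In neuroblastoma, 50 points is simply one of two patients, and the Table 12 shell shows no interval for that stratum. All of this stands and limits the seriousness. It does not justify leaving a wrong scoring rule in place.

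**Conclusion.** The concern holds. The benefit lists in 2.2.2 and 6.1.1 contradict the response tables in section 6. Read literally, a non-progressing osteosarcoma or non-CNS MRT patient with only non-measurable disease and no CR counts as no benefit, and two analysts could score the same neuroblastoma MR differently.

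The per-patient effects rest only on the enrolment figures. The illustrated rates rest on the two assumed counts. An actual effect also requires one of these responses at the assessment nearest 6 or 12 months, and the SAP does not show whether any patient meets that condition. ATRT patients, patients in CR, and the EFS and OS analyses are not affected. The lists should be fixed before CBR is tabulated, but this does not threaten the primary results.

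**What to change.** In sections 2.2.2 and 6.1.1, replace the two lists with one definition by criteria set:

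- RECIST 1.1 (osteosarcoma, non-CNS MRT): CR, PR, SD or Non-CR/Non-PD
- RANO (ATRT): CR, PR or SD
- INRC (neuroblastoma): CR, PR, MR or SD

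Before finalising, check these against protocol Appendix VI and tabulate the overall-response codes that investigators recorded, by stratum. If a non-progressing code outside the relevant table was used, state explicitly how it is scored so that none is dropped by default.

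The cost is a short change of wording in two sections and one tabulation of existing data.

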h Scans performed outside the four-week screening period as standard of care, are acceptable.

i Females of child-bearing age required a negative pregnancy test prior to entering study.

j Follow-up for participants remaining on study was every 6 weeks for the first 3 months, then every 3 months for up to 2 years from completion of therapy. Patients may need to be seen more frequently than these defined intervals based on their medical needs.

In instances where participants discontinued study drug before completion of therapy, they were encouraged to continue with study follow-up visits as long as such procedures did not pose a risk to the well-being of the patient.

Measurement of effect

Survival Measure

At each study visit (every 28 days) while on treatment, patient study status will be collected. If a patient terminates treatment early, the reason and date will be collected. This includes progressive disease, toxicity or adverse event, and death.

Follow-up for participants remaining on study will be every 6 weeks for the first 3 months, then every 3 months for up to 2 years from completion of therapy.

After treatment completion, patient death or lost to follow up will be collected at follow up visits.

Event Measure

Radiographic progressive disease will be captured in the overall response at each disease assessment as per section 9 of protocol. Clinical progression will be documented during study visits as described above.

Full details of the background to the trial and its design are presented in the protocol.

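### The main clinical benefit rate takes the nearest scan at any distance, so a patient who progressed clinically or died after an early stable scan can count as benefiting at 6 and 12 months

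*SAP*

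**What the plan says.** - **Choice of assessment (SAP section 6.1.1).** The value at 6 and 12 months "post treatment commencement will be the overall response disease assessment closest to 6 or 12 months", counted from first dose, or from enrolment if treatment never started. No window or maximum distance follows.
- **Strategy (section 6.1.1).** The main analysis is treatment policy: "CBR will be estimated for patients regardless early treatment or trial termination". The intercurrent events named are coming off for toxicity and coming off for another treatment. Progression and death are not mentioned.
- **Data used (section 6, Measurement of effect).** "Overall response as determined by the investigator will be used for the secondary efficacy outcome analysis".
- **Where progression is recorded (section 2.7, Event Measure).** Radiographic progression enters the overall response at each disease assessment. For the rest, "Clinical progression will be documented during study visits as described above".
- **Imaging after progression (section 2.7, footnote e to the schedule).** "Follow-up imaging studies are not required if there is documented evidence of overt clinical progression".
- **Response tables (section 6).** The RANO table for ATRT lists, under progressive disease, "Failure to return for evaluation as a result of death or deteriorating condition". The RECIST and neuroblastoma tables shown in the SAP have no such line.
- **Sensitivity analysis (section 6.1.1 and Table 12).** A composite row scores early termination of treatment as no benefit.

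**The concern.** A benefit rate at 6 or 12 months should describe patients who are alive and progression-free then. The nearest-scan rule does not ensure this. Patients enter with stable disease or better (section 2.3), so a stable first scan is a likely result. If the patient then progresses clinically or dies, no further scan need exist, and the old stable scan remains the nearest one to both targets.

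The main CBR row would then report benefit for a patient whom the EFS analysis in section 5.1.1 counts as an event. By the same rule, a patient with documented radiographic progression who later has a stable scan on another therapy can also count as benefiting. CBR is the only secondary endpoint in section 2.2.2, and the strata are small enough for one patient to change the reported rate visibly.

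**Working it through.** The SAP reports no CBR result to reproduce, so the check follows one patient through the stated rule and then sizes the effect.

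**1. Target days.** Section 6.1.1 uses 30.437 days per month.
- Month 6: 6 × 30.437 = 182.6 days.
- Month 12: 12 × 30.437 = 365.2 days.

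**2. One patient.** On-treatment imaging is 2-monthly (section 2.7). Suppose stable disease at day 60, then clinical progression or death with no later scan.
- Distance to month 6: 182.6 − 60 = 122.6, about 123 days.
- Distance to month 12: 365.2 − 60 = 305.2, about 305 days.

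That scan is the only candidate, so it is the closest at both time points and gives benefit twice. A last stable scan at day 122 lies 60.6 and 243.2 days away and also counts twice.

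**3. Missing data.** Section 8 and Table 13 list missing responses. Under the literal rule, any patient with at least one post-baseline assessment has a value at both time points, so the rule itself cannot identify a missing CBR value.

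**4. Effect per patient.** Section 2 (Study Expansion) gives 14 enrolled in MRT/ATRT and 9 in osteosarcoma. Taking all of them as eligible:
- MRT/ATRT: 1/14 = 7.1 points.
- Osteosarcoma: 1/9 = 11.1 points.

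**5. Illustration.** The counts below are assumptions; intervals are exact (Clopper-Pearson) 95%.

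| Stratum, assumed true benefits | 0 misclassified | 1 misclassified | 2 misclassified |
|---|---|---|---|
| Osteosarcoma, 0 of 9 | 0% (0–33.6) | 11.1% (0.3–48.2) | 22.2% (2.8–60.0) |
| MRT/ATRT, 3 of 14 | 21.4% (4.7–50.8) | 28.6% (8.4–58.1) | 35.7% (12.8–64.9) |

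**6. A workable window.** Half of the 3-monthly follow-up interval is 3 × 30.437 / 2 = 45.7, rounded to 46 days.
- Month 6: 183 ± 46 = days 137 to 229.
- Month 12: 365 ± 46 = days 319 to 411.

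Each window spans 93 days inclusive, so scans spaced 56, 61, 91 or 92 days apart always place at least one inside it. Twelve 28-day courses end at day 336, which lies in the second window. The windows do not overlap (229 < 319), so one scan cannot serve both time points.

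**The case against.** - **The literal reading may not be intended.** Section 6.1.1 speaks of imaging at 6 and 12 months, and Table 13 expects missing scans, so closest might mean closest among scans near the time point. That is a fair guess at intent, but nothing in the text bounds the distance, and a programmer following it would select the day-60 scan.
- **ATRT is partly protected.** RANO includes clinical status and treats non-return through death or deterioration as progression. This stands. The 7.1-point figure therefore applies mainly to non-CNS MRT patients, whose number is not given. Even for ATRT, the line helps only if a dated progression is entered without a scan, and section 6.1.1 does not say it overrides an earlier scan.
- **The protocol may hold a fuller rule.** The SAP refers to it for response definitions. Section 6.1.1, however, sets the selection rule itself and does not defer to the protocol for it.
- **The composite row already covers this.** It does for most such patients, because progression and death end treatment, and Table 12 prints it beside the main row. But it also fails patients who stopped early while stable, so it answers a different question and does not make the main row right.
- **Data after a switch of therapy belong to treatment policy.** Agreed. Only stable disease after documented progression is a gap.
- **The size is assumed, and the window is one choice among several.** Both are true. Follow-up imaging may also follow routine practice, so the one-scan-per-window property holds only for on-schedule scans.

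**Conclusion.** The concern holds. As written, the main CBR analysis can count a patient as benefiting at 6 or 12 months after that patient has progressed or died, and so contradict the EFS result for the same patient. Each case adds 11.1 points in osteosarcoma or 7.1 points in MRT/ATRT. The exposure is mainly in osteosarcoma, non-CNS MRT and neuroblastoma.

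The number of affected patients is not in the SAP, so the total effect is unknown and may be nil. The sponsor can count the cases by setting the EFS event dates against the scans selected. The conclusion rests on the SAP text alone. The point should be fixed, but it is confined to a descriptive secondary endpoint and leaves EFS and overall survival untouched.

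**What to change.** In section 6.1.1:

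1. State that documented radiographic or clinical progression, or death, on or before the time point (day 183 or 365) counts as no benefit, whatever the scans show.
2. Otherwise use the closest assessment within a stated window matched to the imaging schedule, for example ± 46 days (days 137–229 and 319–411).
3. Keep patients with no scan in the window and no progression in the denominator as not shown to benefit, and list them in Table 13.
4. Report the nearest-scan version as a sensitivity row in Table 12, beside the existing composite row.

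The cost is a few sentences and a small change to the derivation; the progression and death dates are already needed for EFS. CBR may come out slightly lower, and a stable patient with a missed scan is scored as not shown to benefit. Table 13 and the nearest-scan row make that visible.
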